5.3 Study Restrictions

5.3.1 Concomitant Medications

All concomitant medications taken during the study will be recorded in the electronic case report form (eCRF) with indication, dose information, and dates of administration.

5.3.2 Prohibited Concomitant Medications

Subjects using the following medications will be excluded from the study:

- Drugs that may cause hepatotoxicity as assessed by the PI and/or Sponsor.
- Any antidepressants (e.g., selective serotonin reuptake inhibitors [SSRI], serotonin and norepinephrine reuptake inhibitors [SNRIs]) within 4 weeks of Screening Visit
- NK receptor antagonists within 2 weeks of Screening visit
- Women on tamoxifen (or other estrogen modulating drugs) or receiving
 - Chemotherapy/radiation therapy within 4 weeks of Screening or planned antineoplastic
 - Chemotherapy/radiation therapy
- Drugs or herbal medications that could be associated with hot flash like symptoms including nicotinic acid, calcium channel blockers, clonidine, opioid drugs, black cohosh within 2 weeks of Screening Visit
- Drugs that are highly protein bound e.g., Warfarin and digoxin within 4 weeks of screening visit, use of non-steroidal anti-inflammatory drugs from the time of signing informed consent
- Use of any of the following hormonal treatment before Screening Visit:
 - 1 week or longer for prior vaginal hormonal products (rings, creams, gels)
 - 4 weeks or longer for prior transdermal estrogen alone or estrogen/progestin products
 - 12 weeks or longer for prior oral estrogen and/or progestin therapy
 - 3 months or longer for prior progestin implants and estrogen alone injectable drug therapy
 - 6 months or longer for prior estrogen pellet therapy or progestin injectable drug therapy
- Subjects using the following medications within 2 weeks prior to first dosing (or within 5 times the half-life of that medication, whichever is longer) will be excluded from the study:
 - Inhibitors of CYP3A4 (including but not limited to macrolide antibiotics, HIV protease inhibitor, azole antifungal drugs, cyclosporine, calcium channel inhibitor, cimetidine)
 - Inducers of CYP3A4 (including but not limited to rifampicin, carbamazepine, efavirenz, bosentan, modafinil, St. John's Wort)
- Medications with narrow therapeutic index that are metabolized by CYP3A4 and/or CYP2D6 are not allowed from screening until up to 5 half-lives after last dose of ACER-801 is administered.

Subjects will be required to inform the study investigator of any regularly taken medications (prescription or over the counter (OTC)), including hormone replacement therapy, natural and

herbal products, vitamin, mineral or dietary supplement, taken within 2 weeks (or less than 5 times the half-life of that medication, whichever is longer) prior to first dosing. Use of such medications should be reviewed with the medical monitor and permitted on a case-by-case basis.

5.4 Subject Withdrawal

Subjects are free to withdraw from the study at any time for any reason.

In addition, subjects may be withdrawn from the study by the investigator for the following reasons:

- Aes
- Withdrawal of consent
- Protocol violation
- Lost to follow-up
- Other
- If it is in the subject's best interest according to the investigator

The clinical study report will include the reason(s) and relevant details(s) for subject withdrawals.

5.5 Stopping Criteria for Subject Dosing

Study drug will be withdrawn from the subject if the following stopping criteria are met:

- $5 \geq$ ULN ALT/AST and total bilirubin ≤ 2 ULN BILI
- $3 \geq$ ULN ALT/AST and total bilirubin ≥ 2 ULN BILI

5.6 Study Termination Criteria

The Sponsor or designee will review pooled and individual subject data during the course of the study. A single occurrence of the following safety events will trigger an ad hoc meeting to review individual cases:

- Hepatic toxicity such as marked elevations in transaminases or simultaneous elevations in hepatic transaminases and bilirubin (i.e., Hy's Law)
- Severe renal impairment
- Severe cardiovascular dysfunction such as arrhythmia or other abnormalities as indicated by ECG readings

If the Sponsor or its designee determines that the event is drug-related and a clear safety signal has been identified, early termination of the study may occur.

6 TREATMENT OF SUBJECTS

6.1 Investigational Product Treatment Regimen

ACER-801 will be prepared by the pharmacist at the clinical study site.

ACER-801 is only available as a 50 mg capsule. To maintain the blind, subjects randomized to 50 mg and 100 mg ACER-801 will also receive placebo capsules for a total of 4 capsules BID to match the total number of capsules used for the 200 mg BID treatment group (Table 2).

Table 2 Dosing Assignment

Randomization	Morning		Evening	
	ACER-801	PBO	ACER-801	PBO
	# of capsules	# of capsules	# of capsules	# of capsules
50 mg BID	1	3	1	3
100 mg BID	2	2	2	2
200 mg BID	4	0	4	0
Placebo BID	0	4	0	4

6.2 Reference Product

The reference product used in this study will be placebo-matched controls. Placebo-matched controls will look identical to ACER-801 capsules.

6.3 Treatment Compliance

Study drug will be administered as described in Section 6.1, Section 6.2, and the Pharmacy Manual. A witness from the study team will verify that the treatment has been ingested and this information will be recorded in source documentation for each subject.

The quantity received, dispensed, returned, used, lost, etc. will be recorded on the dispensing log provided for the study.

6.3.1 Return/Disposition of Clinical Supplies

Unused study drug must be kept in a secure location for final accountability and reconciliation by Acer or its designee. The investigator must provide an explanation for any destroyed or missing study drug or study materials.

Unused study drug may be destroyed on site, per the clinical unit's standard operating procedures (SOPs), but only after Acer or its designee has granted approval in writing. Acer or its designee must account for all study drug in a formal reconciliation process prior to study drug destruction. If study drug is destroyed on site this must be documented, and documentation must be provided to Acer or its designee and retained in the investigator's study files. The clinical unit should return unused study drug only if instructed to do so by Acer or its designee. The return of study drug or study drug materials must be accounted for on a Study Drug Returns Form provided by Acer or its designee.

All study drug and study drug materials should be stored, inventoried, reconciled, and destroyed or returned according to applicable state and federal regulations, study procedures and applicable SOPs.

6.4 Randomization and Blinding

Subjects will be blinded to the study drug and will be randomized 1:1:1:1 to ACER-801 50 mg BID, 100 mg BID, 200 mg BID or placebo.

6.4.1 Unblinding Procedures

The patient, the Investigator, and other members of the staff involved with the study will remain blinded to study treatment. The study treatment blind shall not be broken by the investigator/designee unless information concerning the study medication is necessary for the medical treatment of the subject. For unblinding a subject, the randomization information for unblinding can be obtained by contacting the clinical site pharmacist (or designee).

6.5 Assignment of Site and Subject Numbers

When a subject is successfully enrolled and randomly assigned to treatment, they will receive a unique identification number and their personal identification (name other identifying information) will be protected, however, the sponsor (or designee) and regulatory authorities have authorization to review source documents which may contain identifying information of study subjects.

6.6 Subject Management

6.6.1 Confinement

Subjects will be housed in the clinical unit from Day -1 until Day 16.

6.6.2 Meals and Dietary Restrictions

Subjects must refrain from eating grapefruit, grapefruit juice, Seville oranges and pomelos within 7 days prior to Day -1 until after their final follow-up visit. Other than this restriction subjects should maintain their usual diet when not in the clinic.

Subjects are required to fast from overnight prior to dosing (approximately 8 hours) prior to Screening and Day 16.

Subjects are required to fast from overnight approximately 8 hours prior to Screening and Day -1.

Subjects will be required to fast overnight for approximately 12 hours on Day 1 and Day 14 and continue to fast until 4 hours post dose.

Subjects will be required to fast overnight prior to morning dosing (approximately 8 hours) on Days 2, and 7. Water will be allowed ad libitum. No fasting is required on Days 3- 6 or Days 8-13 or 15.

7 VISIT PROCEDURES

An informed consent form (ICF) must be signed before any study-related procedures are performed. The AE reporting period will begin at the time the ICF is signed. The treatment-emergent AE (TEAE) reporting period will begin at the time study drug is first administered on Day 1 of the study.

7.1 Screening Procedures (Day -28 to Day -1)

Within 28 days of Day -1, after subjects have provided a signed voluntary written ICF, subjects will be screened for enrollment into the study. The following study evaluations will be performed at screening:

- Written informed consent
- Inclusion/exclusion criteria
- Document fasting period (minimum of 8 hours)
- Concomitant medication review
- Medical history and demographic data
- Urine drug screen
- Virology testing
- Physical examination
- Vital signs
- Weight
- Height (determine BMI for eligibility)
- 12-lead ECG (for safety)
- Biochemistry, Hematology, and coagulation
- Urinalysis
- FSH for eligibility
- Instructions for continuous hot flash diary
- Continuous hot flash diary reporting for 2 weeks prior to randomization (including hot flashes during the day and night)
- Daily recording of bedtime and morning wake up time for 2 weeks prior to randomization.
- AE monitoring (after the ICF has been signed)

The screening visit assessments must be performed within 28 days prior to Day -1 to determine whether the subject meets all the inclusion criteria and none of the exclusion criteria. Subjects who do not fulfill all eligibility criteria will not be enrolled in the study.

7.2 Check-In Procedures (Day -1)

The AE reporting period will begin at the time of the signing of the ICF and continues through the Follow-up phone call.

Subjects will be admitted to the CRU where they will reside from Day -1 to Day 16. All study procedures, including study drug administration, will occur in the CRU. On Day -1, the following procedures will be performed:

- Check-in to clinical unit (start of confinement in clinical unit)
- Confirmation of inclusion/exclusion criteria
- Collect continuous hot flash diary information to confirm eligibility
- Document fasting period (minimum of 8 hours)
- Concomitant medication review
- Medical history
- COVID-19 test
- Vital signs
- Weight
- 12-lead ECG (for safety)
- Urine drug screen
- Serum pregnancy testing
- Electrocardiographs using the Mortara Surveyor (time and duration of ECG collection must be identical on Day -1, Day 1, and Day 14 and must be planned in relation to predose and 15 hrs postdose PK time points)
- Daily recording of bedtime and morning wake up time.
- Biochemistry, hematology, and coagulation
- Continuous hot flash diary reporting (including hot flashes during the day and night)
- LH
- Urinalysis
- AE monitoring
- Randomization can occur on Day -1 or Day 1 (prior to dosing)

7.3 Daily Study Procedures (Day 1 through Day 16)

Subjects will be instructed to perform the below procedures during the study.

Reporting of hot flashes and nighttime awakenings are to be performed independently without consultation with other study subjects or staff unless there is a question regarding initial instructions.

- Concomitant medication review
- Continuous hot flash diary reporting (including hot flashes during the day and night)
- Daily recording of bedtime and morning wake up time
- Vital signs
- AE monitoring
- Administer study drug in the morning (am) and the evening (pm) (Day 1 am through Day 14 pm)

7.4 Day 1 (Confined to CRU)

In addition to study procedures outlined in Section 7.3, all study procedures must be performed prior to morning study administration unless otherwise indicated.

- Document fasting period (minimum of 12 hours) prior to administration of morning study drug and 4 hours after dosing
- Randomization (prior to dosing on Day 1 or Day -1)
- Physical exam

- Electrocardiographs using the Mortara Surveyor (duration and time of collection must be the same on Day -1, Day 1, and Day 14)
- Blood bone density markers
- Biochemistry, hematology, and coagulation
- Catecholamines, vasopressin, gonadotropins, prolactin, insulin collection
- Estradiol, testosterone, SHBG, ACTH, cortisol, TSH, T3 (Total and Free), T4 (Total and Free), FSH collection
- LH assessment
- PK assessment (30 min predose)

Post morning dose:

- 12-lead ECG (for safety) (1-hour post-morning dose)
- PK assessments
- LH assessment (every 60 mins starting at 60 minutes after dose 0 to 8 hrs)

7.5 Day 2

In addition to study procedures outlined in [Section 7.3](#), all study procedures must be performed prior to morning study administration unless otherwise indicated.

- Confirm fasting (8 hours prior to dosing)
- LH assessment
- PK assessment (30 min predose)

Post morning dose:

- LH assessment (every 60 mins starting at 60 minutes after dose 0 to 8 hrs)

7.6 Day 7

In addition to study procedures outlined in Section 7.3, all study procedures must be performed prior to morning study administration unless otherwise indicated.

- Confirm fasting (8 hours prior to dosing)
- Biochemistry, hematology, and coagulation
- Urinalysis
- PK assessment (30 min predose)

7.7 Day 14/End of Treatment

In addition to study procedures outlined in Section 7.3, all study procedures must be performed prior to morning study administration unless otherwise indicated.

- Confirm fasting (minimum of 12 hours prior to administration of morning study drug and 4 hours after)
- Electrocardiographs using the Mortara Surveyor (duration and time of collection must be the same on Day -1, Day and Day 14)
- Biochemistry, hematology, and coagulation
- Blood bone density marker concentration
- Catecholamines, vasopressin, gonadotropins, prolactin, insulin collection

- Estradiol, testosterone, SHBG, ACTH, cortisol, TSH, T3 (Total and Free), T4 (Total and Free), FSH collection
- Urinalysis
- LH assessment
- PK assessment (30 min predose)
- Removal of mortara surveyor after completion of procedures

Post morning dose:

- PK assessments (post morning dose)
- LH assessment (every 60 mins starting at 60 minutes after dose 0 to 8 hrs)

7.8 Day 15

In addition to study procedures outlined in [Section 7.3](#), the following study procedures will be performed.

- 24-hr PK blood draw (relative to the morning dose on Day 14)

7.9 Day 16/ET

In addition to study procedures outlined in Section 7.3, the following study procedures will be performed.

- Confirm fasting (8 hours prior to lab draws)
- Physical exam
- Weight
- 12-lead ECG (for safety)
- Biochemistry, hematology, and coagulation
- Catecholamines, vasopressin, gonadotropins, prolactin, insulin collection
- Urinalysis
- 48-hr PK sample (relative to the morning dose on Day 14)
- Discharge

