7.10 End-of-Study Procedures for Subjects that Withdraw from the Study

Subjects that withdraw from the study must have all EOS/early termination (ET) procedures performed. Subjects should be encouraged to remain at the clinical unit until Day 16 for EOS/ET procedures. The purpose of this visit is to conduct final assessments on or as near as possible to the final day of dosing.

7.11 14-Day Safety Follow-Up

All subjects will be contacted by telephone 14 days (± 4 days) following the final dose of study drug on Day 14. The subject will be queried regarding their overall health and well-being. This telephone contact may be used to verify the resolution of any AEs that were ongoing at the time of the Day 16/ET visit. Any follow-up deemed medically necessary will be conducted as an unscheduled/safety visit, detailed in [Section 7.12](#).

Abnormal lab findings will be closely monitored by the Sponsor and repeated as deemed necessary until resolution and followed up by the treating physician. All safety data will be

reviewed by the Sponsor for any potential safety signals that would alter the safety profile of the molecule.

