The total amount of blood taken for the entire study will be approximately 508 mL.

Table 5 List of Clinical Laboratory and Other Analytes to be Tested

Assessment	Analyte
Central Laboratory (Clinical Site)	
Hematology	Hemoglobin, hematocrit, white blood count with differential (neutrophils, lymphocytes, monocytes, eosinophils, basophils), platelet count, red blood cell count (including mean corpuscular volume, mean corpuscular hemoglobin, mean corpuscular hemoglobin concentration)
Coagulation	Prothrombin time, partial thromboplastin time, international normalized ratio
Serum chemistry	Albumin, alkaline phosphatase, total bilirubin, ALT, AST, blood urea nitrogen, calcium, carbon dioxide, chloride, potassium, sodium, total cholesterol, creatinine, gamma glutamyl transferase, glucose, lactate dehydrogenase, phosphorus, total protein, uric acid
Virology	HIV antibody types 1 and 2, HCV antibody, HbsAg
Peptides	Neurokinin B
Hormones	Catecholamines, vasopressin, gonadotropins, estradiol, testosterone, FSH, LH, ACTH, cortisol, TSH, T3 (Total and Free), T4 (Total and Free), prolactin, SHBG, and insulin
Bone Density markers	BSAP, osteocalcin, amino terminal propeptide of type 1 collagen (P1NP) and Collagen Type- C-Telopeptide (CTX)
Urinalysis	pH, specific gravity, protein, glucose, ketones, bilirubin
Drugs of abuse, cotinine, and alcohol	Drugs of abuse including cocaine, amphetamines, barbiturates, opiates, benzodiazepines, cannabinoids, methadone, cotinine (nicotine), and alcohol
Pregnancy test	Serum pregnancy test
COVID-19 screen	As per site policy.
PK Laboratory	
PPD	ACER-801, metabolite

Note: Blood samples may also be used for the assessment of tachykinin peptides, including NKB, NKA, and substance P.

Abbreviations: ACTH = adrenocorticotrophic hormone; ALT = alanine aminotransferase; AST = aspartate aminotransferase; BSAP = Bone specific alkaline phosphatase COVID-19 = coronavirus disease 2019; FSH = follicle stimulating hormone; HbsAG = hepatitis B surface antigen; HCV = hepatitis C virus; HIV = human immunodeficiency virus; LH = luteinizing hormone; PK = pharmacokinetic; SHBG = sex hormone binding globulin; TSH = thyroid-stimulating hormone; T3 = triiodothyronine; T4 = thyroxine.

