12.3.2 Safety Endpoints

Safety endpoints are:

- Clinically significant changes in physical examination findings at Week 2 relative to Baseline
- Clinically significant changes in clinical laboratory evaluations (hematology, coagulation, serum chemistry, urinalysis, hormones, bone density markers) during the 2-week treatment period relative to Baseline
- Adverse events $\geq 5\%$
- All SAEs and discontinuations

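### A woman who leaves the study before the Day 14 draw has no scheduled post-baseline bone markers or second hormone panel, because the early-termination list omits both

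*Combined protocol and SAP*

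**What the plan says.** Section 12.3.2 lists among the safety endpoints "Clinically significant changes in clinical laboratory evaluations (hematology, coagulation, serum chemistry, urinalysis, hormones, bone density markers) during the 2-week treatment period relative to Baseline". The synopsis places the same item under the primary endpoints. Table 5 (Section 11.3.7) shows what counts as a hormone: "Catecholamines, vasopressin, gonadotropins, estradiol, testosterone, FSH, LH, ACTH, cortisol, TSH, T3 (Total and Free), T4 (Total and Free), prolactin, SHBG, and insulin".

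The draws are set out in Section 7 and Table 1:

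- Day 14 (Section 7.7) includes "Blood bone density marker concentration" and "Estradiol, testosterone, SHBG, ACTH, cortisol, TSH, T3 (Total and Free), T4 (Total and Free), FSH collection". Section 7.4 lists the same two sets on Day 1 before dosing.
- Neither set appears at Day 2 or Day 7 (Sections 7.5 and 7.6).
- The Day 16/ET list in Section 7.9 has one hormone line: "Catecholamines, vasopressin, gonadotropins, prolactin, insulin collection". It has no bone markers. Table 1 agrees.

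For women who withdraw, Section 7.10 says: "Subjects that withdraw from the study must have all EOS/early termination (ET) procedures performed". Footnote 11 of Table 1 likewise directs them to the early-termination assessments. Section 7.10 adds: "Subjects should be encouraged to remain at the clinical unit until Day 16 for EOS/ET procedures".

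**The concern.** The Day 16 list suits a completer, who had the bone markers and the second hormone panel two days earlier. The same list also serves as the early-termination list, and a woman who leaves before Day 14 has not had those tests since her baseline sample. Nothing in the protocol brings the Day 14 draws forward for her.

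Hormones and bone markers are named components of a primary safety endpoint, and changes in them are also exploratory endpoints (Sections 12.5.1 and 12.5.4). For the omitted analytes, change from baseline can be computed only for women still attending on Day 14. Section 5.4 lists adverse events among the reasons for withdrawal, so the women without values could include some whose results matter for safety. Section 7.10 says the visit is meant to capture final assessments close to the last dose; for these analytes it captures nothing.

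**Working it through.** The plan states no figure to reproduce here. The check is a comparison of lists, followed by simple arithmetic on arm size.

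**Inventory.** Counting total and free T3 and T4 separately, Table 5 has 17 hormone entries and 4 bone markers (BSAP, osteocalcin, P1NP, CTX). The schedule comes from Sections 7.4 to 7.9 and Table 1 with its footnote 7.

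| Set | Entries | Day 1 predose | Postdose Days 1 and 2 | Day 14 | Day 16/ET |
|---|---|---|---|---|---|
| Bone markers | 4 | yes | no | yes | no |
| Second hormone panel | 11 | yes | no | yes | no |
| Catecholamines, vasopressin, gonadotropins, prolactin, insulin | 5 | yes | no | yes | yes |
| LH | 1 | yes | yes | yes | not listed separately |

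The hormone rows sum to 11 + 5 + 1 = 17.

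**Coverage for a woman who leaves before the Day 14 draw and attends the ET visit.**

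- Bone markers with a scheduled post-baseline value: 0 of 4.
- Hormone entries from the ET draw: 5 of 17, plus LH from Day 1 postdose and, if she is still present, Day 2.
- Entries with no scheduled post-baseline value: 4 + 11 = 15. The protocol does not define gonadotropins as a line item. If that draw supplies FSH, the count is 4 + 10 = 14.

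**Share of an arm.** Section 12.1 plans 10 to 14 women per arm. One early leaver is 1/14 = 7.1% to 1/10 = 10% of an arm.

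**How many women.** The documents give no dropout rate, so the rates d below are assumptions. The expected total is N × d with N = 40 to 56. The chance of at least one early leaver in a given arm is 1 − (1 − d)^n with n = 10 to 14; for d = 5% and n = 10 this is 1 − 0.95^10 = 0.401.

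| Assumed d | Expected early leavers, whole study | Chance of at least one in a given arm |
|---|---|---|
| 2% | 0.8 to 1.1 | 18% to 25% |
| 5% | 2.0 to 2.8 | 40% to 51% |
| 10% | 4.0 to 5.6 | 65% to 77% |
| 20% | 8.0 to 11.2 | 89% to 96% |

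**After the fix.** The ET visit would cover 4 of 4 bone markers and 5 + 11 = 16 of 17 hormone entries. LH, the seventeenth, already has early postdose samples.

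**The case against.** The strongest reply is that the gap is narrow. Five of the Table 5 hormone entries are drawn at early termination, and LH is sampled hourly after dosing on Days 1 and 2. A reader might infer that an early leaver has no post-baseline hormone data at all; that is wrong. This stands, and it confines the point to the bone markers and the second panel.

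Stopping drug is also not the same as leaving the study. Section 5.5 withdraws study drug without saying that the subject leaves the visit schedule, so a woman who stops dosing but stays could have the Day 14 draw. It does not follow that every early stopper lacks these values. This stands too.

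One could read the heading Day 14/End of Treatment as applying whenever treatment ends. Table 1 gives end of treatment and early termination separate columns, and Section 7.10 and footnote 11 name only the latter for withdrawals, so this reading is weak.

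Sections 7.12 and 11.3.7 allow additional tests, which could well be used for a woman who stops because of an adverse event. They are discretionary, so they help the individual case but do not give uniform endpoint data.

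Finally, dosing lasts 14 days in a confined unit, the safety analysis is descriptive, and Section 12 defers detail to a later SAP. Few women may be affected, and the SAP can state how missing values are handled. It cannot supply a sample that was never scheduled.

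**Conclusion.** The point holds for women who leave the study before the Day 14 draw. They have no scheduled post-baseline value for any of the four bone markers or for 10 or 11 of the 17 hormone entries, although Section 12.3.2 names both classes. The result rests on reading Sections 7.4 to 7.10 and Table 1 as written, and on whether gonadotropins includes FSH.

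Each such woman is 7.1% to 10% of an arm. The number of such women cannot be derived from the documents and may be small.

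A reader might also infer that the missing values are tied to the outcome, so that the dose-group summaries are biased towards women who tolerated the drug. That is plausible but not shown. The documents give no link between these analytes and discontinuation, no withdrawal rate by dose, and in Section 2.2 a similar adverse event incidence on osanetant and placebo in completed trials. This is a modest gap in a named safety endpoint, worth closing because closing it is cheap.

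**What to change.** In Sections 7.9 and 7.10 and in Table 1, state that if a subject leaves before the Day 14 draw, the second hormone panel and the bone density markers scheduled for Day 14 are also collected at the early-termination visit. Record clock time, fasting duration and time since last dose. State whether the gonadotropins line includes FSH.

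In the SAP, report these results as the last post-baseline value, flagged by time since last dose and distinguishable from Day 14 values. They should not automatically be labelled on-treatment. Section 7.10 encourages withdrawn women to stay until Day 16, so a woman whose last dose was on Day 3 could be sampled 16 − 3 = 13 days later. If the sponsor prefers not to add the draw, the plan should say how the endpoint is assessed without it.

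The cost is a few extra millilitres of blood (an assumption; the documents give no volume per panel) at a visit that already takes blood, in early leavers only, for analytes already in Table 5. It stands in for a Day 14 draw that these women missed. The drawback is comparability: footnote 3 of Table 1 requires a 12-hour fast for CTX on Days 1 and 14 but about 8 hours for Day 16, and clock time may differ from Day 1, which matters for analytes with a daily rhythm.
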